		Age at screening up to 180 days of age. Must be able to demonstrate antigravity strength in both biceps. Must have or agree to have placement of feeding tube for enteral access via nasogastric (NG), nasojejunal (NJ), percutaneous gastrostomy (PEG), or percutaneous jejunostomy (PEJ) tube for dosing branaplam (required for the first administration only, and subsequently only for patients who cannot be dosed orally; tube may be removed between doses).
	8. 9.	Minimum CHOP INTEND score of 15 at baseline Must be able to swallow solid and liquid even if tube feeding is used to support nutrition intake and must be the 5 th percentile for length or weight on the international growth curves and must be proportional in height and weight At birth gestational age >32 weeks and body weight at birth >2 kg Able to complete all study procedures, measurements and visits; and parent or guardian/patient has adequately supportive psychosocial circumstances, in the opinion of the Site Investigator.
	Part 3	Written informed consent must be obtained from the parent /
	2.	guardian Current participation in Part 1 or Part 2 of the study protocol and completion of at least 52 weeks of treatment with branaplam Further treatment with branaplam is in the best interest of the patient as assessed by the Site Investigator Able to complete all study procedures, measurements and visits; and parent or guardian/patient has adequately supportive psychosocial circumstances, in the opinion of the Site Investigator
Exclusion criteria	Part 1	payant and an an an analysis and an
EXCIDSION CHEEN	1. 2. 3.	Use of other investigational drugs within 14 days Neurologic or neuromuscular conditions other than SMA. Anemia (Hgb < 9.5 gm/dl ; <5.9 mmol/L), leukopenia (CTCAE Grade 2 or higher, <3000 /mm³; <3.0 x10 9 /L), neutropenia (Grade 2 or higher, <1,500/mm³; < 1.5 X 10 9 /L) or thrombocytopenia (CTCAE Grade 2 or higher, ≤ 75,000/mm³), ≤75 X 10 9 /L

Novartis

- Hepatic dysfunction (AST or ALT CTCAE Grade 1 or higher, ≥ Upper Limit of Normal (ULN)); total bilirubin CTCAE Grade 1 or higher. ≥ ULN).
- 5. Age adjusted renal dysfunction with eGFR calculated using the following formula:

eGFR (in mL/min/1.73 m²) = $0.45 \times Length$ (cm) ÷ serum creatinine (mg/dl) (Schwartz and Work 2009),

- ≤ 26 mL/min/1.73 m² up to age 28 days of age
- ≤ 30 mL/min/1.73 m² for 1 to 3 months of age
- ≤ 40 mL/min/1.73 m² for 3 to 6 months of age
- ≤ 50 mL/min/1.73 m² for 6 to 12 months of age

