- 2. Patients who have received nusinersen at any time prior to screening
- 3. Neurologic or neuromuscular conditions other than SMA.
- Anemia (CTCAE grade 2 of higher Hgb < 1.0 g/dl; <6.2 mmol/L); leukopenia (CTCAE Grade 2 or higher, <3000 /mm³; <3.0 x10⁹/L), neutropenia (Grade 2 or higher, <1,500/mm³; < 1.5 X 10⁹/L) or thrombocytopenia (CTCAE Grade 2 or higher, ≤ 75,000/mm³), ≤75 X 10⁹/L
- 5. Hepatic dysfunction (AST or ALT CTCAE Grade 1 or higher, ≥ ULN); total bilirubin CTCAE Grade 1 or higher, ≥ ULN).
- 6. Age adjusted renal dysfunction with eGFR calculated using the following formula: eGFR (in mL/min/1.73 m2) = 0.45 X Length (cm) ÷ serum creatinine (mg/dl) (Schwartz and Work 2009), ≤ 26 mL/min/1.73 m² up to age 28 days of age ≤ 30 mL/min/1.73 m² for 1 to 3 months of age ≤ 40 mL/min/1.73 m² for 3 to 6 months of age ≤ 50 mL/min/1.73 m² for 6 to 12 months of age
- 7. Clinically significant abnormalities in hematology or clinical chemistry parameters, as assessed by the Site Investigator, at screening that would render the patient unsuitable for inclusion
- 8. Intractable epilepsy
- 9. Persistent (in the opinion of the Investigator) hypoxemia (O₂ saturation awake <92% or O₂ saturation asleep <91%, without ventilation support).
- 10. Presence of an untreated or inadequately treated active infection requiring systemic antiviral or antimicrobial therapy at any time during the screening period.
- 11. Current diagnosis of cardiac and/or vascular abnormalities including uncontrolled hypertension, intolerance of blood pressure and pulse assessment techniques such that consistent normal values cannot be measured, echocardiographic abnormalities (both structural and function) or ECG abnormalities (such as long QT, heart block or Torsade's) indicating significant risk of safety for infant patients participating in the study such as: Concomitant clinically significant pediatric cardiac arrhythmias, e.g. sustained ventricular tachycardia, and clinically significant second or third degree AV block. Clinically significant findings identified by an echocardiogram performed at screening
- 12. Prohibited Concomitant Medications used to treat SMA: oral albuterol or oral salbutamol, hydroxyurea, riluzole, valproate, carnitine, creatine, sodium phenylbutyrate within 14 days prior to enrollment or during the study

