3.5 Rationale for dose/regimen and duration of treatment

3.5.1 Doses in Part 1

Starting dose: Due to the life-threatening nature of the Type I SMA disease, a starting dose must be selected which is intended to be safe but has the potential to show pharmacologically active effects e.g., SMN2 splice modulation. Therefore, an oncology approach was used to calculate the starting dose (14 References, International Council for Harmonization (ICH) S9 guidelines 2010) Doses were adjusted for body surface area since the toxicological reference studies in rats and dogs were done in juvenile animals.

In juvenile rats the highest dose evaluated was 10 mg/kg/day (60 mg/m²/day), and neither lethality nor severe toxicity were observed at this dose; therefore, this dose is considered the rat STD10 (severely toxic dose in 10% animals). The Highest Non-Severely Toxic Dose (HNSTD) in juvenile dogs is considered to be 10 mg/kg/day (200 mg/m²/day). Since 1/10th the rat STD10 scaled for body surface area is not severely toxic in dogs, which is the most sensitive species, the rat data are considered most appropriate for calculating the human starting dose.

The starting dose in patients is 1/10th of the rat STD10 (60 mg/m²/day) = 6 mg/m²/day. Assuming that a pediatric patient of 6.5 kg body weight and 62 cm has a body surface of 0.32 m²,

(using the DuBois formula of BSA= $0.007184*W^{0.425}*H^{0.725}$) (DuBois and DuBois 1916), the starting dose for the first-in-human patient should be 6 mg/m²/day x 0.32 m² ≈ 1.9 mg/day or approximately 0.3 mg/kg. The actual dose of each patient will be adjusted based on weight and length. Similarly, the dose in the extension may be adjusted based all available exposure data.

To uphold pediatric clinical trial guidance, the prospect for direct clinical benefit is built into this study design for all enrolled patients. Thus, the study design has a starting dose that is projected to be minimally efficacious and allows for dose escalation that is not limited by the enrollment pace of a sizeable cohort of patients with a rare disease. Once a patient has been treated for 13 weeks (end of part 1) and enters extended treatment, a patient *may* be switched to a higher dose once this higher dose has been deemed safe in other patients.

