The safety cutoff applies to safety analyses only. The only exception to this are serious adverse events and deaths. Any SAEs occurring after the 30 days period, where a causal relationship to study treatment is suspected, will be reported. All deaths will be reported irrespective of safety cutoff.

In general, treatment emergent AEs are defined as events starting after the first dose of study drug that were absent pre-treatment, or events present prior to the first dose but increased in severity after the first dose. This assumes the same AE with increased severity is properly entered as a separate record in the database with start date being the date when severity increases and that a second AE with same severity won't be entered before the same AE is resolved.

For any other safety analyses based on post-baseline abnormalities compared to baseline (i.e. ECGs, vital signs, etc.), where either of the results is not available, the '**missing**' category will be included to avoid any abnormalities being overlooked.

When showing values over time, for subjects who prematurely discontinued the study, study completion visit assessments will be displayed as if they had occurred at the next scheduled visit.

The eGFR is calculated using the MDRD formula. $eGFR [mL/min/1.73 m^2] = 175 \times (\text{serum Creatinine [umol/L]/88.4}) - 1.154 \times (\text{age [years]}) - 0.203 \times (0.742 \text{ if female}) \times (1.212 \text{ if African American})$ ([Levey et al. 2007](#)).

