2.3.2 Background and demographic characteristics

Summary of baseline demographic characteristics will include:

- Age
- Sex
- Predominant race
- Ethnicity
- Weight
- Length
- Body surface area
- Chest circumference
- Head circumference

Summary of other baseline characteristics will include:

- Mean supine SBP
- Mean supine SBP categories
 - < 130 mmHg
 - >= 130 mmHg
- Mean supine DBP
- Mean supine DBP categories
 - < 80 mmHg
 - >= 80 mmHg
- Mean supine pulse
- Paradoxical breathing assessment,
- eGFR per MDRD formula categories
 - < 30 mL/min/SA
 - >= 30 to < 60 mL/min/SA
 - >= 60 to < 90 mL/min/SA
 - > 90 mL/min/SA
- QTcF

■ [REDACTED]

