5.3 Laboratory parameters derivations

For each subject, the estimated creatinine clearance values (without collecting urine) will be calculated using the Cockcroft-Gault formula (as specified in [Table 5-3](#)). In these calculations, the body weight is the last measurement collected on or before the day when the subject takes the laboratory test and age should also be calculated based on the time when the subject takes the laboratory test.

If the creatinine value is collected in the unit $\mu\text{mol/L}$ (SI unit), it will be converted to mg/dL in order to use the formulas. The conversion is via the equation below:

- $\text{mg/dL} = 88.4 \mu\text{mol/L}$ (e.g., creatinine = 2.0 $\text{mg/dL} = 176.8 \mu\text{mol/L}$).

Table 5-3 Creatinine clearance calculation

Variable	Formula
Creatinine clearance [mL/min] using Cockcroft-Gault formula (Cockcroft and Gault 1976)	$= (140 - A) \times W / (72 \times C) \times G$ Where A is age [years] W is body weight [kg] C is the serum concentration of creatinine [mg/dL] G is a constant: G=1 for males and G=0.85 for females.

The estimated creatinine clearance will be included as one of the laboratory parameters.

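### MDRD puts every eligible infant in the top baseline eGFR category, and unindexed Cockcroft-Gault clearance mixes growth into the change from baseline

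*SAP*

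**What the plan says.** Three renal formulas appear in the two documents.

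- **Protocol, eligibility** (summary, Part 1 exclusion 5 and Part 2 exclusion 6; Section 4.2.2): "eGFR (in mL/min/1.73 m2) = 0.45 X Length (cm) ÷ serum creatinine (mg/dl"). An infant is excluded at or below 26 (up to 28 days), 30 (1 to 3 months), 40 (3 to 6 months) or 50, the last band being "for 6 to 12 months of age".
- **SAP 2.1.1 and 2.3.2, baseline**: "The eGFR is calculated using the MDRD formula", reported as "eGFR per MDRD formula categories". The bands are below 30, 30 to below 60, ">= 60 to < 90 mL/min/SA", and above 90.
- **SAP 5.3 and Table 5-3, over time**: "the estimated creatinine clearance values (without collecting urine) will be calculated using the Cockcroft-Gault formula", in mL/min and with the current weight. "The estimated creatinine clearance will be included as one of the laboratory parameters". SAP 2.8.4 summarises laboratory parameters as change from baseline by visit window.

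The visible text of SAP Section 4, on changes from the protocol, does not mention a renal formula.

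**The concern.** Protocol Table 3-1 lists renal toxicity as a potential risk, Section 3.8 traces it to kidney findings in dogs, and safety laboratory parameters are among the primary endpoints of every part. The SAP's two renal derivations contain age in years, and Cockcroft-Gault contains body weight as well. In infants these terms can dominate the result. Two things could follow. The baseline table may be unable to separate infants at all. The clearance followed over time may rise because the child grows, even when creatinine is rising.

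**Working it through.** **Check of the documents' own figures.** 2.0 mg/dL × 88.4 = 176.8 µmol/L, as in SAP 5.3. Protocol 3.5.1, "using the DuBois formula of BSA" for 6.5 kg and 62 cm, gives 0.317 m², stated as 0.32. Both reproduce.

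**Part A: MDRD at the eligibility limits.** The highest creatinine an eligible infant can have is SCr = 0.45 × length / limit (mg/dL). MDRD = 175 × SCr^-1.154 × age^-0.203, times 0.742 for girls. The exponents are read as superscripts lost from the text. The 1.212 factor is left out because it only raises the result. Lengths of 50 to 72 cm are assumed.

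| Limit (age) | Girls | Boys |
|---|---|---|
| 30 (1 to 3 months) | 157–300 | 212–404 |
| 40 (3 to 6 months) | 191–334 | 257–450 |
| 50 (6 to 7 months) | 239–376 | 322–506 |

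For limit 26 (7 to 28 days, assumed 46 to 56 cm) the ranges are 227–377 and 306–508.

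The minimum is a girl of 3 months at 72 cm: SCr = 0.45 × 72 / 30 = 1.08, so MDRD = 175 × 0.742 × 1.08^-1.154 × 0.25^-0.203 = 157. Eligibility is checked at screening, but the SAP baseline is the last value before dosing. For this infant to reach 90, creatinine would have to rise (157.4/90)^(1/1.154) = 1.62-fold in between.

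By contrast, at 62 cm and 4 months, creatinine of 0.2, 0.3, 0.4, 0.5 and 0.6 mg/dL gives a length-based eGFR of 140, 93, 70, 56 and 47, spread over three bands. MDRD for the same values runs from 1040 down to 293 in girls and from 1401 down to 394 in boys, all in one band.

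**Part B: growth in Cockcroft-Gault.** CG = (140 − age) × weight / (72 × SCr) × G. For one child, G and the starting creatinine cancel in the ratio. Change = growth factor / creatinine fold − 1, so a value drops below baseline once the creatinine fold exceeds the growth factor.

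Assumed first-year growth: 6 to 9 kg, 62 to 74 cm, 3 to 12 months.

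- Unindexed: (139 × 9) / (139.75 × 6) = 1.49
- DuBois BSA: 0.307 to 0.414 m², a factor of 1.351, so indexed: 1.49 / 1.351 = 1.10
- Length-based: 74 / 62 = 1.19

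| Creatinine fold | Unindexed CG | Length-based | BSA-indexed CG |
|---|---|---|---|
| 1.0 | +49% | +19% | +10% |
| 1.4 | +7% | −15% | −21% |

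Between 1.19- and 1.49-fold, unindexed Cockcroft-Gault rises while the length-based eGFR per 1.73 m² falls.

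Pooled Part 1 range (Protocol 5.1.2: 5 to 11 kg, 60 to 88 cm, 2 to 17 months): the unindexed factor is 2.18. BSA goes from 0.277 to 0.511 m² (×1.846), so the indexed factor is 1.18. If creatinine doubles, the changes are 2.18/2 − 1 = +9% unindexed and 1.18/2 − 1 = −41% indexed. The equation is the same, so the missing scaling causes the difference.

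**The case against.** Several points on the other side stand.

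- **Absolute clearance may properly rise with growth.** Table 5-3 defines Cockcroft-Gault in mL/min. A reader might infer that clearance rises while renal function as such falls. That holds only on a size-adjusted scale, and only when creatinine rises within the range shown.
- **The growth inputs are not one child's data.** The Part 1 range is pooled over 13 patients, and no child is shown to span it. The first-year example is assumed.
- **The safety signal does not depend on either equation.** Serum creatinine and its shift tables are analysed directly. Creatinine grades drive the dose-limiting toxicity criteria (Protocol Table 5-6) and the interruption rules (Table 5-7). A reader might infer that renal toxicity would go undetected or that participants are at risk, but the documents do not support that.
- **The clearance output is thinly specified.** SAP Table 5-4 lists creatinine but not clearance, so the output rests on one sentence in 5.3. Shift tables use local laboratory ranges, and none is given for a calculated clearance. Descriptive change from baseline is therefore the output most likely to be affected.
- **Both Part 2 dose groups grow**, so the comparison between doses is affected less than the change within a group.
- **No protocol analysis is breached.** A reader might call the SAP a departure from the protocol, but the protocol sets its length-based formula for eligibility only.

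These points limit the harm. They do not make the baseline table informative or remove growth from the clearance trend.

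**Conclusion.** The point holds and is minor. For infants who meet the renal limits, MDRD leaves three of the four baseline bands empty by construction. This rests on the assumed lengths and on creatinine not rising 1.62-fold or more, in the lowest-scoring case, between screening and baseline. Change from baseline in unindexed Cockcroft-Gault is confounded by growth. In the assumed first-year example it rises 49% at constant creatinine, and it moves opposite to the length-based eGFR for creatinine rises of 1.19- to 1.49-fold. These percentages do not depend on the starting creatinine, but they do depend on the assumed growth. What is affected is one descriptive baseline line and one derived laboratory parameter, in a study whose parts are all stated to be non-confirmatory.

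**What to change.** **Baseline (SAP 2.1.1, 2.3.2).** Replace MDRD with the protocol's length-based eGFR, 0.45 × length / serum creatinine, summarised as a continuous variable. If the 30/60/90 bands are kept, write the top one as ≥ 90, because a value of exactly 90 now falls in none.

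**Over time (SAP 5.3).** Drop the unindexed Cockcroft-Gault clearance. Then either report the length-based eGFR up to 12 months of age (the last age band in the protocol's limits), using the last length on or before the laboratory date, or index the estimate to BSA. Show either one beside serum creatinine.

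**Cost.** SAP wording and one derivation, with no new data. By SAP Tables 2-8 and 2-11, 16 of 17 Part 1 and 13 of 14 Part 2 laboratory windows share a target day with a body-length window. The exception in both is Day 3, which can use the Day 1 length.

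**Downsides to state in the SAP.**

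- The length-based value also rises with growth, by about 19% in the first-year example against 10% for BSA-indexed Cockcroft-Gault. On this count indexing does better. The length-based formula has the advantage of sharing a scale with eligibility and baseline.
- The 12-month stop is a choice; the protocol gives it only as an age band for exclusion. For the oldest entrants, with Day 1 fourteen days after screening, it covers 7 of 14 Part 2 windows (180 days old at screening) and 9 of 17 Part 1 windows (7.0 months).
- Part 3 requires at least 52 weeks of earlier treatment. With the 12-month stop, essentially all its laboratory visits have no renal estimate and rely on serum creatinine and its shift tables.
- Baseline chemistry at Day −2 to −1 would use the screening length. After 28 days of age the band below 30 stays empty for eligible infants.

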2.1.2 Visit windows

Visit-windows will be used for both efficacy and safety data summaries by visit. Visit windows define a time period "around" the targeted visit date as defined in the evaluation schedule of the clinical study protocol. Visit-windows are non-overlapping and defined without gaps between consecutive visit windows. The width of visit windows may vary over the course of the study period.

The purpose of visit windows is to analyze data based on the actual study days (rather than "nominal" visits). E.g., if a subject's Week 3 visit is delayed; it is possible that the Week 3 data be re-aligned to visit-window Week 5 and be summarized under Week 5.

- For **efficacy analyses** all nominal visits (i.e. excluding unscheduled visits) will be mapped into one of the defined visit-windows.
- For **safety analyses** all nominal visits (i.e. excluding unscheduled visits) will be mapped into one of the defined visit-windows. Data from unplanned visits and unscheduled visits will not be re-mapped to other visits for the purpose of displaying variables over time except for laboratory data. For laboratory data, a time window will be used to identify the assessment closest to the target day within the window over time. The unplanned and unscheduled visits will be used in the analysis of event endpoints, and will be counted towards shift tables or other analyses regarding the worst observed values for patients.

It is possible that more than one assessment of a subject fall into a particular visit-window. [Section 2.1.3](#), deals with the statistical approaches to handle multiple visits in a given visit-window.

Tables displaying summary statistics “by visit” will also use the term *visit-window* as column header; this is to remind the reviewer that multiple assessments of a subject might be summarized. [Table 2-1](#) up to Table 2-12, provide visit-windows definitions for applicable parameters in Part 1 and Part 2.

In all scenarios, later visits in Part 1, Part 1 & 3 and/or visits in Parts 2 & 3, will be treated in a similar fashion to those displayed, so that days between visits are divided evenly, without any gaps. The target day is number of weeks * 7 – 6. For Part 1, after week 26 visit, the extended treatment period (as per protocol Table 7-2) is repeated. For example, for CHOP-INTEND, after week 26 visit, there are week 32 (+6 weeks) and week 39 (+7 weeks) visits.

Note: When deriving week 52 visit-window for Part 2 data, the upper bound of the week 52 visit-window will be ignored in order to make sure we do not miss any week 52 Part 2 data. Indeed, data collected by visit are assumed to be Part 3 assessments if visit numbers are \geq IFC ('Consent for additional follow-up study phase') visit number.

For the visit windows for monthly assessments in Part 3, Table 2-13 uses the following logic: planned day -13 days for the start of visit window and +14 days for the end of the visit windows.

Day 0 in Tables 2-13 and 2-14 corresponds to the date of informed consent 'Consent for additional follow-up study phase', which is the first visit of Part 3.

Note: some assessments were collected only every 3 months in Part 3 (e.g. CHOP-INTEND, HINE-2). For those endpoints, please display in summary statistics tables only planned visits for Part 3 (as per protocol).

Part 3 visits will be appended to whichever part the subject came from (i.e. Parts 1 & 3 and Parts 2 & 3).

Table 2-1 Visit windows for CHOP INTEND

Visit-window	Part 1 Day			Part 2 Day		
	Start	Target	End	Start	Target	End
Week 6	1	36	60	1	36	60
Week 13	61	85	106	61	85	106
Week 19	107	127	151	107	127	151
Week 26	152	176	200	152	176	197

Week 32	201	218	242	198	218	242
Week 39	243	267	291	243	267	287
Week 45	292	309	333	288	309	333
Week 52	334	358	382	334	358	382

Table 2-2 Visit windows for HINE

Visit-window	Part 1 Day			Part 2 Day		
	Start	Target	End	Start	Target	End
Week 6				1	36	60
Week 13				61	85	106
Week 19	107	127	151	107	127	151
Week 26	152	176	200	152	176	197
Week 32	201	218	242	198	218	242
Week 39	243	267	291	243	267	287
Week 45	292	309	333	288	309	333
Week 52	334	358	382	334	358	382

Table 2-3 Visit windows Acceptability and Palatability Questionnaire

Visit-window	Part 1 Day			Part 2 Day		
	Start	Target	End	Start	Target	End
Week 2				1	8	11
Week 3				12	15	18
Week 4				19	22	57
Week 14	89	92	95	58	92	95
Week 15	96	99	102	96	99	102
Week 16	103	106	109	103	106	144
Week 27	110	183	186	145	183	186
Week 28	187	190	193	187	190	193
Week 29	194	197	200	194	197	235
Week 40	201	274	277	236	274	277
Week 41	278	281	284	278	281	284
Week 42	285	288	291	285	288	291

Table 2-4 Visit windows for Motor and Speech milestones

Visit-window	Part 1 Day			Part 2 Day		
	Start	Target	End	Start	Target	End
Week 13				61	85	106
Week 19	103	127	151	107	127	151
Week 26	152	176	200	152	176	197
Week 32	201	218	242	198	218	242
Week 39	243	267	291	243	267	287
Week 45	292	309	333	288	309	333
Week 52	334	358	382	334	358	382

Table 2-5 Visit windows for ECG evaluations

Visit-window	Part 1 Day			Part 2 Day		
	Start	Target	End	Start	Target	End
Day 1	1	1	1	1	1	1
Week 2	2	8	46	2	8	46
Week 13	47	85	130	47	85	99
Week 17				100	113	145
Week 26	131	176	221	146	176	190
Week 30				191	204	236
Week 39	222	267	312	237	267	281
Week 43				282	295	326
Week 52	313	358	403	327	358	389

Table 2-6 Visit windows for body temperature and blood pressure/pulse rate/respiratory rate

Visit-window	Part 1 Day			Part 2 Day		
	Start	Target	End	Start	Target	End
Day 2	1	2	2	1	2	2
Day 3	3	3	3	3	3	5
Day 5	4	5	6			
Week 2	7	8	11	6	8	18
Week 3	12	15	18			
Week 4	19	22	25			
Week 5	26	29	32	19	29	43
Week 6	33	36	39			
Week 7	40	43	46			
Week 8	47	50	53			
Week 9	54	57	60	44	57	71
Week 10	61	64	67			
Week 11	68	71	74			
Week 12	75	78	81			
Week 13	82	85	102	72	85	102
Week 18	103	120	134	103	120	134
Week 22	135	148	162	135	148	162
Week 26	163	176	190	163	176	193
Week 31	191	211	225	194	211	225
Week 35	226	239	253	226	239	253
Week 39	254	267	281	254	267	284
Week 44	282	302	316	285	302	316
Week 48	317	330	344	317	330	344
Week 52	345	358	372	345	358	372

[figure not shown]

Table 2-8 Visit windows for physical examination, respiratory function, body weight/body length/BSA, head and chest circumference

Visit-window	Part 1 Day			Part 2 Day		
	Start	Target	End	Start	Target	End
Week 2	1	8	11	1	8	18
Week 3	12	15	18			
Week 4	19	22	25			
Week 5	26	29	32	19	29	43
Week 6	33	36	39			
Week 7	40	43	46			
Week 8	47	50	53			
Week 9	54	57	60	44	57	71
Week 10	61	64	67			
Week 11	68	71	74			
Week 12	75	78	81			
Week 13	82	85	102	72	85	102
Week 18	103	120	134	103	120	134
Week 22	135	148	162	135	148	162
Week 26	163	176	190	163	176	193
Week 31	191	211	225	194	211	225
Week 35	226	239	253	226	239	253
Week 39	254	267	281	254	267	284
Week 44	282	302	316	285	302	316
Week 48	317	330	344	317	330	344
Week 52	345	358	372	345	358	372

Table 2-9 Visit-windows for Ulnar CMAP and mRNA blood collection

[figure not shown]
Visit-window	Part 1 Day			Part 2 Day		
	Start	Target	End	Start	Target	End
Week 13	1	85	130	1	85	130
Week 26	131	176	221	131	176	221
Week 39	222	267	312	222	267	312
Week 52	313	358	403	313	358	403

Table 2-10 Visit-windows for ophthalmological evaluations

Visit-window	Part 1 Day			Part 2 Day		
	Start	Target	End	Start	Target	End
Week 12	1	78	123	1	78	123
Week 25	124	169	214	124	169	214
Week 38	215	260	305	215	260	305
Week 51	306	351	396	306	351	396

Table 2-11 Visits windows for Hematology, Blood chemistry, and Urine analysis

Visit-window	Part 1 Day			Part 2 Day		
	Start	Target	End	Start	Target	End
Day 3	1	3	5	1	3	5
Week 2	6	8	11	6	8	18
Week 3	12	15	22			
Week 5	23	29	36	19	29	43
Week 7	37	43	50			
Week 9	51	57	64	44	57	71
Week 11	65	71	78			
Week 13	79	85	102	72	85	102
Week 18	103	120	134	103	120	134
Week 22	135	148	162	135	148	162
Week 26	163	176	190	163	176	193
Week 31	191	211	225	194	211	225
Week 35	226	239	253	226	239	253
Week 39	254	267	281	254	267	284
Week 44	282	302	316	285	302	316
Week 48	317	330	344	317	330	344
Week 52	345	358	372	345	358	372

[figure not shown]

Table 2-13 Monthly visit windows in Part 3

Visit-window	Part 3 Day		
	Start	Target	End
P3 Month 0	0	0	14
P3 Month 1	15	28	42
P3 Month 2	43	56	70
P3 Month 3	71	84	98
P3 Month 4	99	112	126
P3 Month 5	127	140	154
P3 Month 6	155	168	182
P3 Month 7	183	196	210
P3 Month 8	211	224	238
P3 Month 9	239	252	266
P3 Month 10	267	280	294
P3 Month 11	295	308	322
P3 Month 12	323	336	350
P3 Month x	28*x-13	28*x	28*x+14

Table 2-14 Three-monthly visit windows in Part 3

Visit-window	Part 3 Day		
	Start	Target	End
P3 Month 0	0	0	42
P3 Month 3	43	84	126
P3 Month 6	127	168	210
P3 Month 9	211	252	294
P3 Month 12	295	336	378
P3 Month x	28*x-41	28*x	28*x+42

* post-baseline values

Table 2-15 Bin widths for HINE subscale stacked bar charts

Visit-window	Study Day	
	Start	End
>0-3 months	1*	91
>3-6 months	92	182

>6-9 months	183	273
>9-12 months	274	364
>x-x+3 months	$(x/3)^*91+1$	$((x+3)/3)^*91$

* post-baseline values

